# 14.3 Study Files

Documentation concerning Investigator data, IRB data, and clinical laboratory data is required before shipment of oral ifetroban to the study site (Appendix 16.2). Copies of these documents as well as supplemental information, such as the Investigator's Brochure and Responsibilities and Obligations of Investigators and Sponsors (Appendix 16.3.2), will be kept on-site in a special study file. This file also will contain drug accountability (receipt/dispensing) records, Sponsor/Investigator correspondence, IRB correspondence, changes to the protocol, information regarding monitoring activities, subject exclusion records, biological samples records, and CRFs. Investigator data, including FDA Form 1572 and statement of qualifications for each Investigator, are provided in Appendix 16.3.2.

#### 16 APPENDICES

# 16.1 Protection of Human Subjects

Informed consent must be obtained from every subject before he enters a study. It must be given freely and not under duress. Consent must be documented by the subject or the subject's legally authorized representative signing an IRB/IEC-approved consent form. Subjects who do not speak English must be presented with a consent form written in a language that they understand. A copy of the signed consent form must be given to the subject signing it. The original must be kept in the Investigator's files and made available to Sponsor and representatives of the appropriate regulatory authority upon request. If, for any reason, subject risk is increased as the study progresses, a revised, IRB/IEC-approved consent form must be signed by the subject. Before the study begins, a sample of the consent form must be provided to the Sponsor. The appropriate regulatory authority may reject otherwise scientifically valid studies if proper informed consent has not been obtained from all subjects.

#### 16.1.1 Basic Elements Of Informed Consent

Every consent form must include explanations of each of the following 20 elements:

- That the trial involves research
- The purpose of the trial
- The trial treatment(s) and the probability for random assignment to each treatment
- The trial procedures to be followed, including all invasive procedures
- The subject's responsibilities
- Those aspects of the trial that are experimental
- The reasonably foreseeable risks or inconveniences to the subject and, when applicable, to an embryo, fetus, or nursing infant
- The reasonably expected benefits; and when there is no intended clinical benefit to the subject, the subject should be made aware of this
- The alternative procedure(s) or course(s) of treatment that may be available to the subject, and their important potential benefits and risks

- The compensation and/or treatment available to the subject in the event of a trial-related injury
- The anticipated prorated payment, if any, to the subject for participating in the trial
- The anticipated expenses, if any, to the subject for participating in the trial
- That the subject's participation in the trial is voluntary and that the subject may refuse to participate or withdraw from the trial, at any time, without penalty or loss of benefits to which the subject is otherwise entitled
- That the monitor(s), the auditor(s), the IRB/IEC, and the regulatory authority(ies) will be granted direct access to the subject's original medical records for verification of clinical trial procedures and/or data, without violating the confidentiality of the subject, to the extent permitted by applicable laws and regulations and that, by signing a written informed consent form, the subject or the subject's legally acceptable representative is authorizing such access
- That the records identifying the subject will be kept confidential and, to the extent permitted by the applicable laws and/or regulations, will not be made publicly available; and if the results of the trial are published, the subject's identity will remain confidential
- That the subject or the subject's legally acceptable representative will be informed in a timely manner if information becomes available that may be relevant to the subject's willingness to continue participation in the trial
- The person(s) to contact for further information regarding the trial and the rights of trial subjects, and whom to contact in the event of a trial-related injury
- The foreseeable circumstances and/or reasons under which the subject's participation in the trial may be terminated
- The expected duration of the subject's participation in the trial
- The approximate number of subjects involved in the trial

Nothing in these regulations is intended to limit the authority of a physician to provide emergency medical care to the extent the physician is permitted to do so under applicable federal, state, or local laws.

Informed consent allows the subject to fully understand his participation and serves to protect the Investigator and Sponsor from potential negligence claims. A fully informed subject is the best protection against such claims.

The informed consent requirements in these regulations are not intended to preempt any applicable federal, state, or local laws that require additional information to be disclosed in order that informed consent be legally effective. Some states require further action on the Investigator's part concerning subject consent.

### **16.2** Requisite Documents for Approval of Study Site

Oral ifetroban sodium will be provided to the Investigators after they have submitted the following documents to the Study Monitor:

- Signed protocol
- Signed Statement of Investigator or FDA Form 1572 (if required by the regulatory agency)
- Document indicating IRB/IEC approval of the final protocol, the informed consent and/or assent and recruitment advertisement documents (to include name, address, and chairperson of the IRB/IEC)
- Blank copy of the IRB/IEC-approved informed consent document
- Signed Investigator's Agreement and Letter of Confidentiality
- Clinical Laboratory Certification and normal ranges for tests that are performed in the laboratory for study assessments
- *Curricula vitae* for the Investigator and Sub-Investigator(s) (i.e. individuals who, as part of an investigative team, will assist the investigator and make a direct and significant contribution to the data. In general, if an individual is directly involved in the performance of procedures required by the protocol, and the collection of data, that person should be listed on the 1572).
- Financial disclosure Form FDA 3454 (any study FDA relies on to establish that the product is effective or any study in which a single investigator makes a significant contribution to the demonstration of safety).

# 16.3 Responsibilities and Obligations of Investigators and Sponsors

# 16.3.1 Sponsor/Study Monitor

The CPI Study Monitor will:

#### Conduct a pre-investigation Site Selection Visit and/or Study Initiation Visit to:

- Establish the acceptability of the facility and record the visit in a written report (i.e., memorandum or form).
- Discuss with the Investigator the proposed clinical trial and supply draft CRFs, the Investigator's Brochure, and the draft protocol for review and approval.
- Discuss with the Investigator the regulatory requirements with respect to informed consent, IRB/IEC approval of the trial, the protocol, protocol amendments, and changes to the informed consent document.
- Discuss with the Investigator the timing of interim and final reports to the Study Monitor
  and obligation to supply the Study Monitor with copies of all study-related documents
  (including IRB/IEC approval, IRB/IEC charter or equivalent, membership and
  qualifications, protocol amendments, informed consent documents, and consent changes),
  CRFs, CRF changes, and all pertinent correspondence to and from the IRB/IEC.

#### Conduct periodic on-site visit(s) to:

- Assure adherence to the protocol.
- Review CRFs and hospital records for accuracy and completeness of information.
- Examine pharmacy or other IMP storage and dispensing records for documentation of
  quantity and date of receipt of investigational drug, dispensation and accountability data
  for product administration to each subject, loss of materials, contamination, and unused
  supplies.
- Record and report (summarize) observations on the progress of the trial and continued acceptability of the facilities, and prepare an on-site visit report.
- Review Investigator files for required documents, (e.g., protocols; protocol amendments; Investigator's Brochure; Study Procedures Manual; IRB/IEC approval of protocols, amendments, and informed consent documents; IRB/IEC charter and membership; and communications to and from the IRB/IEC and the Study Monitor.

### 16.3.2 Investigator

### **Institutional Review Board/Independent Ethics Committee**

The Investigator must assure the Study Monitor in writing that the Institutional Review Board/Independent Ethics Committee (IRB/IEC):

- Meets FDA 21CFR 56 and/or ICH regulations as defined in ICH E 63: Institutional Review Board/Independent Ethics Committee (as applicable).
- Has the authority delegated by the parent Institution and found in the IRB/IEC by-laws, operation guidelines, or charter to approve or disapprove clinical trials and protocols, including informed consent and other documents (e.g., protocol amendments and information to be supplied to subjects concerning informed consent).
- Complies with proper personnel make-up of the Board.
- Convenes meetings using acceptable rules of order for making decisions, recording such decisions, and implementing them.
- Maintains files that contain (a) documentation of its decisions, such as are found in IRB/IEC minutes and correspondence, (b) written guidelines or by-laws governing IRB/IEC functions, (c) protocol, (d) protocol amendments, (e) approved informed consent document and information to be supplied to the subject, and (f) correspondence between the IRB/IEC and Investigator (e.g., consent changes, protocol amendments).

#### **Informed Consent of Human Subjects**

The Investigator must assure the Study Monitor in writing that the informed consent document for a subject:

- Meets FDA 21CFR part 50 and/or ICH regulations as defined in ICH E6 4.8: Informed Consent of Trial Subjects (as applicable).
- Has been approved by the IRB/IEC, including (when required) information to be given to the subject regarding the trial in which he is enrolled.
- Includes the basic elements and any additional elements of informed consent that are appropriate.

- Has been signed by both the subject and the Investigator or designee, and a copy has been given to the subject.
- May be provided to the subject in the "short form" informed consent document with written information as an alternative.

### **Storage and Dispensing of Product Supplies**

The Investigator (or Pharmacist) must assure the Study Monitor in writing that:

- Adequate and accurate written records show receipt and disposition of all product supplies, including dates, serial or lot numbers, quantities received, and each quantity dispensed, administered, or used, with identification of each subject.
- Purpose and reasons are given in written records for product disposal (e.g., the amount contaminated, broken, or lost) and the quantity that was returned to the Sponsor.

#### **Case Report Forms**

The Investigator must assure the Study Monitor in writing that:

- The completed CRF accurately reflects the hospital records for each subject.
- The CRFs and hospital records will be accessible to the Clinical Monitor during on-site visits.

#### Files and Records

The Investigator must assure the quality, integrity, and content of his files, which will be subject to audit by the Study Monitor and the appropriate regulatory authority inspectors. The files must contain, as minimum:

- Correspondence to and from the IRB/IEC and to and from the Clinical Monitor.
- Documents including the following:
  - o IRB/IEC-approved protocols.
  - o IRB/IEC-approved protocol amendments.
  - o IRB/IEC-approved informed consent/assent documents and information to be supplied to the subject.

- IRB/IEC-approved recruitment advertisement(s)
- o IRB/IEC charter, membership, and qualifications of each member.
- Clinical supplies records including the following:
  - o Receipt, date and quantity, and batch or lot number.
  - o Disposition dates and quantity administered to each subject.
  - o Inventory records.

Documents and records must be retained by the Investigator for a period of two years following the date a marketing application is approved for the product for the indication for which it is being investigated, **OR** If no application is to be filed or if the application is not approved for such indication, until two years after the investigation is discontinued and the appropriate regulatory authority is notified.

# 16.4 22-item Sino-nasal Outcome Test (SNOT-22)

Below you will find a list of symptoms and social/emotional consequences of your rhinosinusitis. We would like to know more about these problems and would appreciate you answering the following questions to the best of your ability. There are no right or wrong answers, and only you can provide us with this information. Please rate your problems as they have been over the past two weeks. Thank you for your participation. Do not hesitate to ask for assistance if necessary.

1. Considering how severe the problem is when you experience it and how often it happens, please rate each item below on how "bad" it is by circling the number that corresponds with how you feel using this scale: →	No Problem	Very Mild Problem	Mild or slight Problem	Moderate Problem	Severe Problem	Problem as bad as it can be	5 Most Important Items
1. Need to blow nose	0	1	2	3	4	5	0
2. Nasal Blockage	0	1	2	3	4	5	0
3. Sneezing	0	1	2	3	4	5	0
4. Runny nose	0	1	2	3	4	5	0
5. Cough	0	1	2	3	4	5	0
6. Post-nasal discharge	0	1	2	3	4	5	0
7. Thick nasal discharge	0	1	2	3	4	5	0
8. Ear fullness	0	1	2	3	4	5	0
9. Dizziness	0	1	2	3	4	5	0
10. Ear pain	0	1	2	3	4	5	0
11. Facial pain/pressure	0	1	2	3	4	5	0
12. Decreased Sense of Smell/Taste	0	1	2	3	4	5	0
13. Difficulty falling asleep	0	1	2	3	4	5	0
14. Wake up at night	0	1	2	3	4	5	0
15. Lack of a good night's sleep	0	1	2	3	4	5	0
16. Wake up tired	0	1	2	3	4	5	0
17. Fatigue	0	1	2	3	4	5	0
18. Reduced productivity	0	1	2	3	4	5	0
19. Reduced concentration	0	1	2	3	4	5	0
20. Frustrated/restless/irritable	0	1	2	3	4	5	0
21. Sad	0	1	2	3	4	5	0
22. Embarrassed	0	1	2	3	4	5	0

SNOT-20 Copyright 1996 by [name]., Washington University School of Medicine, St. Louis, MO SNOT-22 Developed from modification of SNOT-20 by National Comparative Audit of Surgery for Nasal Polyposis and Rhinosinusitis Royal College of Surgeons of England.

### 16.5 PNIFR Methodology

#### Per Celikel 2013:

Traditional NIFR measurements can yield highly variable results. However, assessment of the rate of peak nasal inspiratory flow (PNIF) has recently been shown to be an inexpensive, simple and fast method with good reproducibility.

The PNIF meter is simply an inverted mini-Wright flow meter attached to an airtight face mask. The PNIF is then measured using a Youlten meter (or similar) in liters per minute.

All subjects should be instructed on how to use the Youlten meter properly. All subjects should be seated during testing and encouraged to inhale as hard and fast as they can through the mask while keeping the mouth closed and starting from the end of a full expiration. Two individual NIFR measurements will be taken at all study time points. The two measurements within 5% of each will be recorded. If the measurements are not within 5% of each other, a third measurement will be made and recorded.

# 16.6 Total Nasal Symptom Score (TNSS)

Please answer all the questions to the best of your ability twice daily, once in the morning after waking up and a second time before bedtime.

$0 = NONE \qquad 1 = M$	ILD 2	2 = MO	DERA	ΓE 3	= SEVE	CRE		
	Date:		Date:		Date:		Date:	
	AM	PM	AM	PM	AM	PM	AM	PM
Please rate how your nasal congestion								
has been over the past 12 hours:								
Please rate how your runny nose has								
been over the past 12 hours:								
Please rate how your nasal itching								
has been over the past 12 hours								
Please rate how your sneezing has								
been over the past 12 hours:								
Please rate how difficult has it been								
with nasal symptoms to sleep or go								
about your day's activities:								

### 16.7 Asthma Control Questionnaire –7 (ACQ-7)

Please answer questions 1-6. Circle the number of the response that best describes how you have been during the past week.

- 1. On average, during the past week, how often were you woken by your asthma during the night?
  - 0 Never
  - 1 Hardly ever
  - 2 A few times
  - 3 Several times
  - 4 Many times
  - 5 A great many times
  - 6 Unable to sleep because of asthma
- 2. On average, during the past week, how bad are your asthma symptoms when you wake up in the morning?
  - 0 No symptoms
  - 1 Very mild symptoms
  - 2 Mild symptoms
  - 3 Moderate symptoms
  - 4 Quite severe symptoms
  - 5 Severe symptoms
  - 6 Very severe symptoms
- 3. In general, during the past week, how limited were you in your activities because of your asthma?
  - 0 Not limited at all
  - 1 Very slightly limited
  - 2 Slightly limited
  - 3 Moderately limited
  - 4 Very limited
  - 5 Extremely limited
  - 6 Totally limited
- 4. In general, during the past week, how much shortness of breath did you experience because of your asthma?
  - 0 None
  - 1 A very little
  - 2 A little
  - 3 A moderate amount
  - 4 Ouite a lot
  - 5 A great deal
  - 6 A very great deal

- 5. In general, during the past week, how much time did you wheeze?
  - 0 Not at all
  - 1 Hardly any of the time
  - 2 A little of the time
  - 3 A moderate amount of the time
  - 4 A lot of the time
  - 5 Most of the time
  - 6 All the time
- 6. On average, during the past week, how many puffs/inhalations of short-acting bronchodilator (eg. Ventolin) have you used each day?
  - 0 None
  - 1 1-2 puffs/inhalations most days
  - 2 3-4 puffs/inhalations most days
  - 3 5-8 puffs/inhalations most days
  - 4 9-12 puffs/inhalations most days
  - 5 13-16 puffs/inhalations most days
  - 6 More than 16 puffs/inhalations most days
- 7. (To be completed by staff)

FEV, % predicted:

**Points** 

Points assigned =

- 0 >95% predicted
- 1 90-95% predicted
- 2 80-89% predicted
- 3 70-79% predicted
- 4 60-69 predicted
- 5 50-59% predicted
- 6 <50% predicted

 
Scoring: Sum points from all questions 1-7. Divide this sum by 7
If question 7 is not available, divide by 6.
ACQ score =

Juniper 1999

# 16.8 Adult Equipotent Daily Doses of Inhaled Glucocorticosteroids

Drug	Low Daily dose (µg)	Medium Daily dose (μg)	High Daily dose (µg)
Beclomethasone dipropionate – CFC	200-500	>500-1000	>1000-2000
Beclomethasone dipropionate – H FA	100-250	>250-500	>500-1000
Budesonide	200-400	>400-800	>800-1600
Ciclesonide	80-160	>160-320	>320-1280
Flunisolide	500-1000	>1000-2000	>2000
Fluticasone propionate	100-250	>250-500	>500-1000
Mometasone furoate	200	≥400	≥800
Triamcinolone acetonide	400-1000	>1000-2000	2000

Bachert 2016

# 16.9 Self-assessment of Treatment (Optional)

We would like to better understand your opinion on the treatment you received during the trial. Please, answer the following question. Thank you for your cooperation.

Could you tell us about your opinion regarding the treatment you had during the trial? What did you like or dislike about the treatment?

1. INTRODUCTION

This Statistical Analysis Plan (SAP) is based on study procedures and analyses described in the protocol (dated 24 January 2017). Table shells and mock listings corresponding to the contents of this document will be included with the final version. This document, with table shells and mock listings, will be reviewed prior to any unblinded analyses, and revised if necessary.

2. LIST OF ABBREVIATIONS

Term	Definition
ACQ	Asthma Control Questionnaire
AE	Adverse Event
AERD	Aspirin Exacerbated Respiratory Disease
ANCOVA	Analysis of Covariance
BMI	Body Mass Index
CFB	Change From Baseline
CPI	Cumberland Pharmaceuticals Inc.
CRF	Case Report Form
FeNO	Fractional Exhaled Nitric Oxide
FEV1	Forced Expiratory Volume in 1 second
INR	International Normalized Ratio
ITT	Intent-to-Treat
kg	Kilogram
LOCF	Last Observation Carried Forward
LS	Least Squares
MedDRA	Medical Dictionary for Regulatory Activities
MI	Multiple Imputation
mL	Milliliter
NRI	Non-Responder Imputation
PCFB	Percent Change From Baseline
PP	Per Protocol
PNIFR	Peak Nasal Inspiratory Flow Rate
PT	MedDRA Preferred Term
PT	Prothrombin Time

QoL	Quality of Life
SAE	Serious Adverse Event
SAP	Statistical Analysis Plan
SNOT	Sino-Nasal Outcome Test
SOC	MedDRA System Organ Class
TEAE	Treatment-Emergent Adverse Event
TNSS	Total Nasal Symptom Score
TPr	Thromboxane Prostanoid Receptor
UPSiT	University of Pennsylvania Smell Identification Test

3. STUDY OBJECTIVES

3.1 Primary Objective

Determine the efficacy of ifetroban compared to placebo to improve sino-nasal symptoms and quality of life (QoL) using the Sino-Nasal Outcome Test (SNOT) - 22 score in symptomatic AERD subjects.

3.2 Secondary Objectives

- Evaluate the effect of ifetroban on asthma symptoms by forced expiratory volume 1 (FEV1) compared to baseline.
- Assess nasal symptoms and QoL using the peak Nasal Inspiratory Flow Rate (PNIFR), University of Pennsylvania Smell Identification Test (UPSIT), fractional exhaled nitric oxide (FeNO), Asthma Control Questionnaire (ACQ) - 7 and Total Nasal Symptom Score (TNSS)
- Determine whether ifetroban reduces the frequency and severity of asthma exacerbations and chronic sinusitis as well as the frequency of rescue medication and antibiotic use.
- Evaluate the pharmacodynamic effects of TPr blockade on eicosanoids and eosinophil count.

[figure not shown]

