# 6.4 Secondary Efficacy Endpoints and Other Exploratory Endpoints

# 6.4.1 Second and Exploratory Efficacy Endpoints

- Subject reported symptoms:
  - Asthma Control Questionnaire (ACQ-7)
  - Total Nasal Symptom Score (TNSS)
- FEV1 and peak Nasal Inspiratory Flow Rate (PNIFR)
- University of Pennsylvania Smell Identification test (UPSIT)
- Frequency and severity of asthma exacerbations and chronic sinusitis
- Use of rescue medication and antibiotic use
- Urinary leukotriene E4 and PG metabolite levels
- Serum leukotriene B4 levels
- Blood eosinophil count
- Fractional exhaled Nitric oxide (FeNO)
- Nasal epithelial, urinary and plasma eicosanoid levels

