### 11.6.3.2 Analysis of secondary endpoints

CFB in ACQ-7 and CFB in TNSS at Week 8 will be analyzed using ANCOVA, with the corresponding value at Baseline included as the only covariate. These variables, as well as CFB in SNOT-22, at Week 4 will also be analyzed as ancillary analyses.

Analyses of CFB for other continuous efficacy variables will be performed at Weeks 4 and 8 in the same manner using ANCOVA with the corresponding value at Baseline included as the only covariate.

Any improvement in SNOT-22, ACQ-7, and TNSS (Yes or No) at Weeks 4 and 8 will be analyzed using the normal approximation to the binomial distribution, assuming unequal variances.

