 - CFB ACQ = post-treatment measurement – baseline
 - Any improvement in ACQ-7 (Yes or No): If CFB ACQ<0, then improvement =’Yes’; otherwise improvement = ‘No’
- Total Nasal Symptom Score (TNSS) AM and PM measurements
 - TNSS Daily Score = sum of the 4 symptom scores (congestion, runny_nose, nasal_itching, sneezing) for both AM and PM, separately. (listed only)
 - TNSS Visit Score: The daily score for AM and PM are averaged over time between the visits separately. Baseline Visit Score for AM and PM is obtained by averaging over the screening period and the day of the baseline visit. Week 4 Visit Score is obtained by averaging over the day after the baseline visit to the day of the Week 4 visit. Week 8 Visit Score is obtained by averaging over the day after Week 4 visit to the day of the Week 8 visit. Week 10 Visit Score is obtained by averaging over the day after Week 8 visit to the day of Week 10 visit.
 - CFB TNSS Visit Score = post-treatment measurement – baseline
- Frequency and Severity of Asthma Exacerbations (Respiratory Reaction Questionnaire)
 - Subject Frequency =count the number of reports since the previous visit for each visit
 - CFB Frequency = post-treatment measurement – baseline
 - Max Severity= define the maximum severity for each subject (none, mild, moderate, or severe) over the period since the previous visit.
 - Inhaler or rescue med (number of reports) count= count the number of reports where resp_rxn_inhaler >0 OR resp_rxn_add_tx_yn=Yes
 - CFB Inhaler or rescue= post-treatment measurement – baseline

- Frequency and Severity of Chronic Sinusitis (Sinus Infection Questionnaire)
 - Antibiotic use Frequency (number of reports) count= count the number of reports over the period since the previous visit where sinus_inf_antibio=yes
 - CFB Antibiotic use= post-treatment measurement – baseline

Pharmacodynamic Variables and biomarkers

- Plasma - Data from third party vendor
 - ScD10L (pg/mL)
 - Sp_selection (ng/mL)
- Biomarkers - Data from third party vendor.
 - Urine LTE4 (ng/mg Creatinine)
 - Urine PGD-M (ng/mg Creatinine)
 - Urine TX-M (ng/mg Creatinine)
 - Plasma F2 Isoprostanes (ng/mL)
 - Serum LTB4 (ng/mL)
 - SAM-Eicosanoids PGD2 (ng/mL)
 - SAM-Eicosanoids PXA2 (ng/mL)
 - SAM-Eicosanoids F2 Isoprostanes (ng/mL)

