7.2 Secondary Efficacy Analyses

The analyses performed for the secondary efficacy variables will be combinations of summary statistics and ANCOVAs, using the normal approximation to the binomial (see Appendix A for details.) as appropriate, at specified visits presented in the table below.

The ANCOVA will include the corresponding value at Baseline as the only covariate with treatment. The LS means, standard error and p-values will be presented with corresponding the summary statistics.

Categorical variables will be analyzed using the normal approximation to the binomial distribution, assuming unequal variances. The p-value will be presented along with summary statistics.

The chart below outlines the analyses to be performed on each variable. It identifies the weeks in which the analysis will be performed for the variable of interest, the population, and the type of imputation.

Variable Name	Value Type	Pop	Weeks for Analysis			Imputation (2)
			Summary	ANCOVA	Binomial (1)	
SNOT-22	Score PCFB	ITT	0,4,8,10			LOCF
	Improvement(y/n)	ITT	0,4,8,10		4,8,10	NRI
SNOT-22 Subscale	Nasal Related	ITT	0,4,8,10			LOCF
	Ear and Facial	ITT	0,4,8,10			LOCF
	Quality of Life	ITT	0,4,8,10			LOCF
	Psychological	ITT	0,4,8,10			LOCF
	CFB Nasal Related	ITT	0,4,8,10			LOCF
	CFB Ear and Facial	ITT	0,4,8,10	4,8,10		LOCF
	CFB Quality of Life	ITT	0,4,8,10	4,8,10		LOCF
	CFB Psychological	ITT	0,4,8,10	4,8,10		LOCF
	22 Questions	ITT	0,4,8,10			LOCF
FEV1	Value	ITT	0,4,8,10			LOCF
	CFB	ITT	0,4,8,10	4,8,10		LOCF
PNIFR	Value	ITT	0,4,8,10			LOCF
	CFB	ITT	0,4,8,10	4,8,10		LOCF
UPSIT	Value	ITT	0,4,8,10			LOCF
	CFB	ITT	0,4,8,10	4,8,10		LOCF
FeNO	Value	ITT	0,4,8,10			LOCF
	CFB	ITT	0,4,8,10	4,8,10		LOCF
ACQ	Value	ITT	0,4,8,10			LOCF
	CFB	ITT	0,4,8,10	4,8,10		LOCF
	Improvement (y/n)	ITT	0,4,8,10		4,8,10	NRI

(1) Normal approximation to the Binomial
 (2) Imputation analysis outlined in Section 5.1. NRI=Non responder imputation, LOCF=Last observation carried forward

Variable Name	Value Type	Pop	Analysis			
			Summary	ANCOVA	Binomial (1)	Imputation (2)
TNSS AM/PM	Visit Score	ITT	4,8,10			LOCF
	CFB Visit score	ITT	4,8,10	4,8,10		LOCF
Asthma	Reports	ITT	0,4,8,10			LOCF
	CFB Reports	ITT	0,4,8,10	4,8,10		LOCF
	Max Severity	ITT	0,4,8,10			LOCF
	Rescue report	ITT	0,4,8,10			LOCF
	CFB rescue report	ITT	0,4,8,10	4,8,10		LOCF
Sinusitis	Reports	ITT	0,4,8,10			LOCF
	CFB Reports	ITT	0,4,8,10	4,8,10		LOCF
	Max Severity	ITT	0,4,8,10			LOCF
	Antibiotic report	ITT	0,4,8,10	4,8,10		LOCF

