	CFB Antibiotic report	ITT	0,4,8,10			LOCF
Plasma	ScD10L	ITT	0,4,8,10			LOCF
	Sp_selection	ITT	0,4,8,10			LOCF
Bio-Markers	LTE4	ITT	0,4,8,10			LOCF
	PGD-M	ITT	0,4,8,10			LOCF
	TX-M	ITT	0,4,8,10			LOCF
	F2 Isoprostanes	ITT	0,4,8,10			LOCF
	LTb4	ITT	0,4,8,10			LOCF
	SAM-Eicosanoids PGD2	ITT	0,4,8,10			LOCF
	SAM-Eicosanoids PXA2	ITT	0,4,8,10			LOCF
	SAM-Eicosanoids F2 Isoprostanes	ITT	0,4,8,10			LOCF

(1) Normal approximation to the Binomial
 (2) Imputation analysis outlined in Section 5.1. NRI=Non responder imputation, LOCF=Last observation carried forward

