7.3 Subgroup Analyses

To assess the consistency of treatment effects across the subgroup levels, and to examine baseline biomarkers for their potential value to predict treatment response, exploratory analyses will be conducted for CFB SNOT-22 (imputed using LOCF) for the variables below.

Each covariate will be used in separate regression models for CFB SNOT-22, along with the treatment and interaction. The p-value for treatment and the interaction will be presented. Additional ad-hoc exploratory analyses may be provided based on the results of these analyses; any additional analyses will be presented in a separate report.

Covariate	Pop	Analysis		
		Summary	ANCOVA	ANOVA
Age	ITT		4,8,10	
Gender	ITT			4,8,10
Site	ITT			4,8,10
Race	ITT			4,8,10
Baseline SNOT-22	ITT		4,8,10	
Baseline TNSS	ITT		4,8,10	
Baseline ACQ-7	ITT		4,8,10	
LTE4	ITT	8	8	
PGD-M	ITT	8	8	
TX-M	ITT	8	8	
F2 Isoprostanes	ITT	8	8	
LtBct	ITT	8	8	
SAM-Eicosanoids PGD2	ITT	8	8	
SAM-Eicosanoids PXA2	ITT	8	8	
SAM-Eicosanoids F2 Isoprostanes	ITT	8	8	

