9. CHANGES IN THE STATISTICAL METHODS FROM THOSE STATED IN THE PROTOCOL

The secondary variables will be analyzed with the ITT population only.

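### The SAP keeps a pharmacodynamic secondary objective on eicosanoids and eosinophil count but pre-specifies no between-arm estimate or test for it

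*SAP*

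**What the plan says.** The objective in SAP 3.2 is "Evaluate the pharmacodynamic effects of TPr blockade on eicosanoids and eosinophil count"; the protocol synopsis has the same one.

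Protocol 6.4.1 lists "Blood eosinophil count" among its secondary and exploratory efficacy endpoints, with urinary leukotriene E4 and prostaglandin metabolites, serum leukotriene B4, and nasal, urinary and plasma eicosanoids. Protocol 11.6.3.2 adds a general rule: "Analyses of CFB for other continuous efficacy variables will be performed at Weeks 4 and 8 in the same manner using ANCOVA". The Endpoints entry of the protocol synopsis sorts differently. Its efficacy list is SNOT-22, ACQ-7, FEV1, UPSIT, FeNO, PNIFR and TNSS, and biomarkers fall under safety, tolerability and other exploratory endpoints.

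SAP 4.6, under "Pharmacodynamic Variables and biomarkers", names two plasma markers and eight biomarkers. It defines no change from baseline for any of them and does not mention eosinophils. SAP 7.2 says of its chart: "It identifies the weeks in which the analysis will be performed for the variable of interest, the population, and the type of imputation". The biomarker rows, down to "SAM-Eicosanoids F2 Isoprostanes", carry summary weeks and LOCF but no ANCOVA entry.

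In SAP 7.3 the eight biomarkers do have ANCOVA at Week 8, in this role: "Each covariate will be used in separate regression models for CFB SNOT-22, along with the treatment and interaction". SAP 9 declares one change from the protocol: "The secondary variables will be analyzed with the ITT population only".

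**The concern.** A stated objective should lead to a stated analysis, and here it does not. Protocol 5.3 calls this a proof-of-concept study. Its rationale is that ifetroban prevents cysteinyl leukotriene and PGD2 generation in mice, and Protocol 5.1 adds that longer TPr blockade suppresses eosinophilic inflammation in the mouse model. Whatever SNOT-22 shows, a reader will ask whether these markers moved on drug relative to placebo.

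Under the SAP the answer would come from descriptive tables (SAP 5: n, mean, SD, minimum, median, maximum), with no treatment difference, interval or baseline adjustment. Any formal comparison would be designed after unblinding, with marker, scale and week still open. The protocol may also have promised an ANCOVA that the SAP drops without saying so.

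**Working it through.** **1. The plan's own figure.** The documents give a sample size only for the primary endpoint. With SD 16, difference 12, two-sided 0.05 and 90% power (SAP 4.5), n per arm = 2(1.960 + 1.282)² × 16²/12² = 37.4, so 38. Power at 38 is 0.905 (normal) or 0.897 (t). The figure reproduces and is not in dispute.

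**2. Tracing each variable through the SAP.**

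| Variable | CFB defined in 4.6 | CFB ANCOVA in 7.2 | Elsewhere |
|---|---|---|---|
| FEV1, PNIFR, UPSIT, FeNO, ACQ, TNSS | yes | Weeks 4, 8, 10 | – |
| Eight eicosanoid biomarkers | no | none (summary at 0, 4, 8, 10) | 7.3: predictors of SNOT-22 change |
| Two plasma markers | no | none (summary at 0, 4, 8, 10) | – |
| Eosinophil count | not listed | no row | hematology differential (8.2) |

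Rows with a between-arm estimate or test: 0 of 10, or 0 of 8 counting only the eicosanoid biomarkers. Eosinophil rows in 4.6, 7.2 and 7.3: 0.

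**3. What SAP 7.3 tests.** Its outcome is SNOT-22 change. The biomarker is a covariate, with a treatment interaction. That asks whether a marker predicts response, not whether the drug changes the marker.

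**4. What the schedule supports.** Eicosanoid samples are taken at Weeks 0, 4, 8 and 10. Hematology is drawn at Screening, at Week 0 (may be skipped if screening labs are recent), at Week 8, and at Week 10 only after abnormal Week 8 labs. Week 8 is therefore the only scheduled on-treatment eosinophil count. SAP 5.1 already substitutes the last screening value for a missing baseline.

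**5. Precision of the missing comparison.** No marker SD is given, so results are in SD units and assume that all 38 per arm are evaluable.
- Standard error of a difference = √(2/38) = 0.229 SD.
- Detectable difference at 80% power = (1.960 + 0.842) × 0.229 = 0.64 SD (0.65 with the t distribution). At 90% it is 0.74 SD.
- Power for true differences of 0.3, 0.4, 0.5 and 0.6 SD: 26%, 41%, 59% and 74% (normal approximation).
- 95% CI half-width = 1.993 × 0.229 = 0.46 SD. With 30 evaluable per arm it is 0.52 SD.
- Baseline adjustment multiplies the SD of the on-treatment value by √(1 − ρ²). For an assumed ρ of 0.5 to 0.7, the 80% detectable difference falls from 0.643 to 0.643 × 0.866 = 0.56, or 0.643 × 0.714 = 0.46 SD.

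**6. Number of added comparisons.** Eight biomarkers at two weeks plus eosinophils once = 17. With the two plasma markers, 10 × 2 + 1 = 21. If tested at 0.05 and independent, the chance of at least one false positive is 1 − 0.95¹⁷ = 58% or 1 − 0.95²¹ = 66%. At Week 8 alone, eight biomarkers plus eosinophils give 1 − 0.95⁹ = 37%.

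**The case against.** The objective is to evaluate effects; it promises no test. Descriptive summaries remain, and if they are tabulated by arm a reader could derive an unadjusted Week 8 difference and interval from the means and SDs. Eosinophils may appear in the safety hematology tables, and SAP 8.5 may supply their change from baseline. The table shells, which might say more, are not part of these documents. All of this stands. A reader might infer that the objective cannot be answered at all, and the documents do not support that. What is missing is a pre-specified between-arm estimate or test. A baseline-adjusted or log-scale estimate cannot be recovered from the planned summaries.

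A reader might also infer a clear undeclared breach of the protocol. That is arguable only. On the synopsis list, the other continuous efficacy variables are FEV1, UPSIT, FeNO and PNIFR, and SAP 7.2 gives each its ANCOVA. The Week 4 part of the 11.6.3.2 rule could not be followed for eosinophils anyway, because no count is scheduled then. The synopsis and 6.4.1 disagree on endpoint status, so silence in SAP 9 is not proof of a dropped analysis.

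Blank chart cells alone would be weak evidence, since the nasal subscale change row also lacks an ANCOVA entry. Here, though, the change rows themselves are absent and 4.6 independently defines no change variable.

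Finally, ifetroban is a receptor antagonist. The documents' direct evidence of target effect is inhibition of TPr-induced platelet aggregation (Protocol 5.4). The mouse eicosanoid findings in Protocol 5.3 concern reactions to aspirin, and this trial has no aspirin challenge (Protocol 5.5). Unchanged eicosanoids would not show that the target was missed. This stands and limits what the added analysis can claim.

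**Conclusion.** The gap is real and modest. None of the eight eicosanoid biomarkers, and not eosinophil count, has a pre-specified between-arm estimate or test, although SAP 3.2 keeps them as a secondary objective. The two plasma markers are also summarised only, but nothing in the documents identifies them as eicosanoids, so the point does not rest on them.

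It would be too strong to say that biomarkers enter no ANCOVA, because SAP 7.3 uses them as predictors. It would also be too strong to say that the missing analysis would separate a drug that failed to engage its receptor from one that engaged it without benefit. It would show whether the measured pathway markers changed.

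The precision figures (half-width 0.46 SD, 80% power at 0.64 SD) assume 38 evaluable per arm and say what the comparison could deliver; they do not measure harm. The primary analysis is unaffected. The change is worth making because it is cheap and lets the trial address its own objective.

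**What to change.** Before unblinding:

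- **SAP 4.6 and 7.2, eicosanoid markers.** Define change from baseline for each marker and add an ANCOVA with treatment and baseline at Weeks 4 and 8.
- **SAP 4.6 and 7.2, eosinophil count.** Add it as a variable, taken from the five-part differential, with the same model at Week 8 only, using the screening value where Week 0 was not drawn.
- **Scale.** Where data are skewed, analyse log post-baseline minus log baseline, with log baseline as covariate. Taking the log of the change itself would fail for zero or negative changes. State how zero counts and values below quantification are handled.
- **Reporting.** Give the treatment difference, or the geometric mean ratio on the log scale, with a 95% CI. Label these analyses exploratory, with no multiplicity-controlled claims.
- **SAP 9.** Reconcile the synopsis with Protocol 6.4.1 and 11.6.3.2 on whether biomarkers are efficacy variables, and record the decision.

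The cost is SAP wording and added table output; no new samples are needed. The downside is about 20 more exploratory comparisons, which is why estimates with intervals should lead rather than p-values.
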